A lack of expertise of primary care providers in the assessment of risk and difficulty linking patients to needed resources may also pose significant barriers for providers in screening processes. Integrated tools for risk assessment and referral for follow-up of positive IPV screening, including reminders of legal conditions that may mandate disclosure (for example, children witnessing IPV events), may help providers feel more comfortable with screening tasks [5, 10], and thus encourage compliance with screening guidelines. While screening and counseling for IPV is a billable activity, the desire to keep discussions private may result in a provider not using IPV-related billing codes and losing potential credit for time spent counseling in provider productivity calculations. An approach to document time spent in confidential activities that a health system might *choose not to bill for* because of privacy concerns may be important positive reinforcement for provider screening behaviors for IPV.

The objective of this paper is to describe the protocol of a stepped wedge cluster randomized trial for evaluating the effectiveness an IPV screening workflow consisting of three major components:

1. a non-interruptive alert for annual IPV screening;
2. PVS confidential screener;
3. Provider risk assessment of PVS screening results and patient referrals.

Stepped wedge study design was chosen for several reasons [11]. Firstly, we had a background control condition present (nurse-led screening) in all clinics. Secondly, because each cluster acts as its own control we need a limited set of clusters to reach the desired level of statistical power. We also needed time to do staff trainings and intervention support, and make sure that they follow our intervention protocol, with stepped wedge design we could do trainings in 5 clinics at a time. In addition, this design gives us control over temporal trends in the data.

METHODS/DESIGN

Study design/Participants

The protocol for this study is based on a stepped wedge cluster randomized controlled trial design [12].

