28 clinics (14 Family Medicine, 12 Internal Medicine Primary Care and 2 women's health clinics) are grouped into 3 blocks each holding 8-12 clinics based on number of eligible patients seen in 2018-2019 and the number of full-time employees in clinics to assure that each block has similar population and employee size. We then use random number generator to randomize the starting time for 3 blocks. The target population is all women aged 18-49 who visit the clinics during the whole study period. Multiple screenings of the same patient can be made as it is described in the Intervention section. The blocks are shown in Figure 1.

Control (nurse-led screen)	Intervention Start (nurse-led and confidential screen)		
Time Period 0	Time Period 1	Time Period 2	Time Period 3

Q1 2020 – Q2 2020	Q3 2020 – Q4 2020	Q1 2021 – Q2 2021	Q3 2021 – Q4 2021
28 clinics	8-12 clinics 16-20 clinics	16-20 clinics	28 clinics

Figure 1. Randomized Stepped Wedge design with 28 clinics.

The control condition is a nurse-led screen developed by MUSC and deployed in 2019. When patients are roomed in all outpatient clinics, nurses complete a checklist where they, based on professional judgment (e.g., without asking standardized questions), screen for a variety of factors. One of those factors is Abuse/Neglect. Clicking on this item in the Epic EHR user interface, opens a second menu for nurses to document either the absence of any evidence of abuse/neglect or the presence of different risk factors. Selecting the “caregiver degrades or threatens patient”, “abuse/neglect suspected”, “evaluation for abuse”, “excessive fear/withdrawn or guarded behavior” or “has unexplained injuries or bruises” was considered a positive screener for spousal abuse risk. It is important to note that control screening is always present (though not necessarily completed) when patient is eligible for confidential screening intervention, thus two screens are working at the same time during intervention period.

IRB determined that this was a quality improvement effort which did not require consent identifying and managing IPV is part of current practice the intervention was the Epic automatic fielding and special protection approaches used that decreased patient risk of disclosure.

Intervention

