Table 1. How IPV Positive patients were identified using both screens.

Screen type	IPV Positive	IPV Negative
Nurse-led screening	
One or several of the following answers is selected by during assessment for Abuse/neglect:
 
• Has unexplained injuries, bruises, cuts• Caregiver degrades or threatens patient• Abuse/neglect suspected• Being evaluated for suspected abuse	
One or several of the following selected:
 
• No suspicion of abuse or neglect• Poor hygiene, dirty/unkept inappropriate clothing• Excessive fear, withdrawn, or guarded behavior• Non-compliance with plan of care
Confidential screening	
In case one of the following answers was given:
 
• Have you been hit, kicked, punched, pushed, shoved, or otherwise hurt by someone at home in the past year? Yes• Do you feel safe in your current relationship? No• Is there a partner from a previous relationship who is making you feel unsafe now? Yes	
In case when the following answers were given:
 
• Have you been hit, kicked, punched, pushed, shoved, or otherwise hurt by someone at home in the past year? No• Do you feel safe in your current relationship? Yes, or Not applicable.• Is there a partner from a previous relationship who is making you feel unsafe now? No

Power Calculations

This study will involve a total of n=28 clinics which will provide two years of data on approximately 68,000 patient visits. Of these, we expect 34,000 to occur during the non-screening steps and 34,000 visits during the intervention period.

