Based on our current practice visit patterns for unduplicated visits by women between age 18 and 49 years, we will have approximately 34,000 eligible visits during the non-screening steps and 34,000 during the screening steps. We have assumed an annual IPV prevalence of 5.5% within the preceding year, based on rates reported by the CDC for SC [17], a screening completion rate of 95%, a 75% counselling rate for women who screen positive, and a 50% referral rate to the Hotline. Studies report the ability of screening to increase patient referral to services from a 2.5 percentage point to an 8.0 percentage point increase based on current referral rates between 0% and 3.6% [18]. Based on an analysis of our archival data, we expect that our current referral rate for IPV for women aged 18-49 seen in our clinics is no more than 0.14% and that this rate will increase to 3.9% with screening.

With about 600 relevant patient visits over 6 months per clinic, 8-12 clinics per wedge, and 3 wedges, we estimate that we will have 97% power to detect an increase in screening (i.e. 0.14% vs. 5.5%), and 89% power to detect a difference in the rate of referral for counseling and/or calls to the Domestic Violence Hotline (i.e. 0.14% vs. 3.9%). While we may be somewhat overpowered for our primary analysis, these numbers of clinics and patients will also allow us to make very precise estimates of the treatment effects within relevant patient subgroups (e.g. whites vs. blacks, urban vs. rural) and to determine whether there are any differential impacts of the intervention on those subgroups. These power calculations are conducted using PASS15 (NCSS, Kayesville, UT) and verified using the 'steppedwedge' function in STATA (StataCorp, College Station, TX), assumed an intraclass correlation coefficient of 0.05 (to account for a moderate level of clustering of patients within clinics), along with an alpha of 0.05 and two-sided testing.

Statistical analysis

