We will use a generalized linear mixed model with a logit link controlling for block set and a fixed effect for each step, as discussed by Hussey and Hughes [19], to compare active screening accounting for the cluster design with a random clinic effect. Primary analyses will also adjust for patient characteristics (age, race) since these have been associated with risk of IPV. Models will be estimated with interaction terms to assess subgroup effects for specific patients, and to examine the effect of practices' characteristics on the heterogeneity of the estimates.

The intraclass correlation coefficients will also be estimated and reported for screening and counselling to assess the assumptions made for the sample size analyses so that this information will be available to future investigations using similar designs and outcomes.

Analysis for the other outcomes will be largely description. Frequency tables with patient demographics, including race, insurance, ethnicity, age, and marital status will be reported. Responses to individual PVS questions will also be presented in the form of frequency tables. Danger 5 risk assessment will be presented using histogram showing counts of patients that scored 0 to 5 of the risks [16]. Physician compliance will be measured as percentage of screened positive patients for whom decision-support templates have been based. Rates of referrals will be reported as percentage from total of patients screened positive.

In addition, we will perform sensitivity analyses to assess the effects of early vs. late randomization, potential “learning” effects that may occur as the screening becomes better integrated in practice routines, the effect of the practices’ presence of a IPV champion prior to the study, and the effect for practice-specific screening refusal and rate of counselling acceptance on the overall estimate. Sensitivity analyses for the primary and secondary outcomes will be conducted using several methods, which have different missing data assumptions: 1) Complete case analyses which assumes missing data are completely at random; 2) Multiple imputation using $M=10$ imputations, which assumes missing at random; and 3) Assigning contrasting age group, race and income category classifications for missing values differentially by intervention group, which aligns with non-ignorable missingness (the data missingness is nonrandom and related to the actual values.)

Follow-up interview

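### Only the order of three pre-formed blocks is randomised, but power and standard errors count 28 clinics, so time changes shared within a block are not allowed for

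*Combined protocol and SAP*

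**What the plan says.** Study design/Participants says that the clinics "are grouped into 3 blocks each holding 8-12 clinics based on number of eligible patients seen in 2018-2019" and on staff numbers, so that the blocks are alike in size. The next sentence is "We then use random number generator to randomize the starting time for 3 blocks". No random assignment of single clinics is described. Figure 1 shows four half-year periods, with all clinics in control first and one block switching at each of the three later periods.

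Power Calculations starts from "This study will involve a total of n=28 clinics" and continues "With about 600 relevant patient visits over 6 months per clinic, 8-12 clinics per wedge, and 3 wedges". It uses one intraclass correlation of 0.05, for patients within clinics.

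Statistical analysis states: "We will use a generalized linear mixed model with a logit link controlling for block set and a fixed effect for each step". It adds a random clinic effect. It lists no block-by-step term, no clinic-by-step effect, no small-sample correction and no randomisation-based test.

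Among the reasons for the design, the end of Background offers "because each cluster acts as its own control we need a limited set of clusters to reach the desired level of statistical power". It also says that the design deals with trends over time.

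**The concern.** The unit that chance acts on is the block, of which there are three. The unit that the analysis treats as independent is the clinic, of which there are 28. The block term removes stable differences in level between blocks. It does not remove a change that affects one block's clinics together at one step, and all clinics in a block switch at the same time. Such a change is partly read as intervention effect, with a standard error that reflects only variation between clinics.

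Every stepped wedge assumes that its sequences share a time pattern. The usual protection is that many units are randomised to sequences, so that differing trends balance by chance and show up in the residual variation. With three randomised units that protection is nearly absent. What Background says about time trends then holds only if the three blocks follow one time pattern, and the plan neither states nor examines this.

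**Working it through.** **Inputs from the documents.** 28 clinics, 3 blocks and 4 periods (Study design/Participants); about 600 visits per clinic per period, about 68,000 visits in all with 34,000 per condition, ICC 0.05, two-sided alpha 0.05, and rates of 0.14% vs 5.5% and 0.14% vs 3.9% (Power Calculations). Assumed here: a 5% event rate, blocks of about 28/3 = 9.33 clinics, and the block-by-step and clinic-by-step SDs.

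**1. The plan's power.** Use effective n = n / [1 + (m − 1) × 0.05] and a two-proportion test.
- n = 34,000 and m = 68,000/28 ≈ 2,428 give effective n = 278 and power of 97.0% and 88.5%.
- n = 14 × 600 = 8,400 and m = 600 give effective n = 271 and power of 96.7% and 87.8%.

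Both agree with the stated 97% and 89%. That the figures were obtained in this way is an inference. Both versions treat the 28 clinics as independent clusters, with no allowance for block-level randomisation. (The Hussey-Hughes stepped-wedge variance with 28 clinics gives over 99.9% for both.)

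**2. Possible allocations.** Three blocks have 3! = 6 orders. Single clinics allocated 9/9/10 would have 28!/(9! 9! 10!) ≈ 6.4 × 10^11 allocations before balance constraints.

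**3. What the model can separate, on the 12 block-period cells.**

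| Terms | Rank without treatment | Rank with treatment |
|---|---|---|
| Block + step | 6 | 7 |
| Block + step + linear block trends | 8 | 9 |
| Block × step, unrestricted | 12 | 12 |

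The effect is estimable under a common time pattern and under linear block trends. It is wholly aliased with unrestricted block-by-step changes.

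**4. Type I error when a block shares a shock.** On the log-odds scale, the variance per clinic-step is v = 1/(600 × 0.05 × 0.95) + 0.2² = 0.0351 + 0.0400 = 0.0751, where 0.2 is the assumed clinic-by-step SD. With block-by-step SD s, the true variance of the effect is proportional to v + 9.33 s². A clinic-level analysis has 112 − 32 = 80 residual degrees of freedom, of which only 12 − 7 = 5 lie between block-period cells. Its estimated variance therefore averages v + (5/80) × 9.33 s². Let r be the square root of true over estimated variance. Type I error is then about P(|t| > 1.99/r).

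| s | True | Estimated | r | Approximate type I error | Simulated |
|---|---|---|---|---|---|
| 0 | 0.075 | 0.075 | 1.00 | 5% | 5% |
| 0.1 | 0.168 | 0.081 | 1.44 | 17% | about 18% |
| 0.2 | 0.448 | 0.098 | 2.13 | 35% | about 35% |
| 0.3 | 0.915 | 0.128 | 2.68 | 46% | about 45% |

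Repeat simulations gave 17–18%, 35–37% and 45–47%. With clinics randomised individually, the same shocks gave 5–6%.

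**5. Dependence on the other assumption.** With no clinic-by-step variation, v = 0.0351 and the approximation gives about 27% at s = 0.1 and 45% at s = 0.2. A separate simulation on the risk scale, also without that variation, gave 28% at 0.5 percentage points and 49% at 1.1 points. For comparison, s = 0.1 is 0.1 × 0.05 × 0.95 ≈ 0.5 points.

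**6. Shocks independent between clinics.** These leave type I error at about 5% if the standard error allows for them. The planned model does not. It would take 0.0351 as the variance where 0.0751 applies, so r = √(0.0751/0.0351) = 1.46 and type I error is about P(|Z| > 1.96/1.46) = 18%.

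**7. Size against the planned effects.** In the three-by-four layout with equal blocks, the treatment column keeps a residual sum of squares of 0.833 after block and step. Shocks of SD 0.3 thus add 0.3/√0.833 = 0.33 to the SD of the estimate. The planned contrasts are 3.73 (0.14% vs 5.5%) and 3.37 (0.14% vs 3.9%) on the log-odds scale, more than ten times as large.

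**The case against.** Much of the case on the other side stands.

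- **Primary outcome.** Outcome measurement defines it as the share of eligible patients who complete the PVS. The PVS is part of the intervention, so completion before roll-out is near zero by construction. Staffing or case mix cannot create PVS completion in a clinic that does not yet have it. The 5% null calculation does not represent this outcome.
- **Shared shocks are assumed.** The blocks are formed on size and are not described as geographic or administrative units. The documents give no reason why the clinics of one block should move together. The balance criteria do omit specialty (14 Family Medicine, 12 Internal Medicine, 2 women's health), which could be a route if the blocks differ in mix. The mix is not given.
- **Aliasing of sequence-by-step with treatment is generic.** Randomising single clinics would not remove a shock caused by the roll-out wave itself.
- **The calculations approximate.** They use a linear model for clinic-step values, not the planned logit mixed model.

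A reader might infer from the six orders that the trial cannot reach significance, because a randomisation test could not go below 1/6 = 0.167. The plan does not use that test, so this is a caveat and not an error in the planned analysis. A reader might also infer that the whole causal claim rests on one draw from six. Step 7 and the nature of the primary outcome do not support that.

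The mismatch between the randomised unit and the analysed unit remains. The planned sensitivity analyses (early against late start, learning effects) do not address it.

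**Conclusion.** The concern holds, with a limited reach. The plan randomises three blocks but bases power and standard errors on 28 clinics with only a random clinic effect, and its claim about time trends needs a common time pattern across blocks. If that fails, intervals are too narrow and p-values too small. The consequence falls mainly on detection of at-risk patients, on subgroup interactions and on confidence intervals, and on referral if it is compared between conditions. A large rise in PVS completion is unlikely to be overturned.

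Type I error of about 18%, 35% and 45% shows direction and sensitivity. It is not a forecast, because it rests on assumed block-by-step SDs of 0.1, 0.2 and 0.3, a 5% event rate and a clinic-by-step SD of 0.2. That the mismatch exists does not depend on these values.

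**What to change.** **If allocation is not yet done.** Randomise the 28 clinics individually to the three start dates by covariate-constrained randomisation. Generate many 9/9/10 allocations, keep those balanced on eligible women, staff size and specialty, and draw one. Add a permutation test over the retained allocations. The number of waves and the size balance are kept. The small cost is that the sponsor cannot choose which clinics share a wave.

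**If allocation is done.** This seems likely, since the steps run from 2020 to 2021 and the reference list includes 2022 and 2023 sources.
- In Study design/Participants, state that the block is the randomised unit.
- In Statistical analysis, add clinic-by-step random effects with a small-sample correction, and a sensitivity analysis with block-specific linear trends.
- In Background, state that control of time trends assumes a common pattern across blocks, and qualify the causal wording to match.

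The cost is a few sentences and somewhat wider intervals. The linear trends themselves cost little. In the equal-block layout the treatment column's slopes by block are −1/6, 1/3 and −1/6, so its residual sum of squares falls by (1/36 + 1/9 + 1/36)/5 = 0.033, from 0.833 to 0.800. The standard error rises by √(0.833/0.800), about 2%, before any loss of degrees of freedom.

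These additions do not cover everything. Clinic-by-step effects deal with shocks that are independent between clinics, and linear trends deal with steady drift. An abrupt change shared by one block stays inseparable from the intervention effect, which is why the wording must also be qualified.

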Methods/Design: A stepped wedge cluster randomized trial across the 28 clinics in three blocks of 8-12 sites will be used to assess the impact of an electronic health record (EHR)-based multifactorial intervention screening for Intimate Partner Violence in primary care practice for women aged 18 to 49 years. Our EHR intervention will promote IPV screening and risk management in primary care and will consist of three components: (1) a non-interruptive EHR alert; (2) confidential screening using the 3-item Partner Violence Screening (PVS) instrument and (3) confidential assessment and referral of high-risk patients using decision-support templates. Efficacy of each of these components will be assessed separately. The trial will be conducted in the setting of a control intervention of screening for IPV using nurse interviews and an electronic checklist.

Discussion: This paper describes the use of a stepped wedge cluster randomized trial to evaluate a privacy preserving screening approach.

BACKGROUND

Intimate Partner Violence (IPV) is a frequently occurring condition (5.9% annual rate of IPV reporting in women in US [1]) for which screening in primary care is the United States Preventative Service Task Force recommended service [2]. The lifetime prevalence of IPV is reported to be 25% of all women [3].

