Referral for IPV further care will be managed in two ways. In settings of immediate risk to the patient there will be immediate outreach to hospital security and a nurse specialist providing IPV support to the Emergency Department. For lower-risk cases, patients are provided psychoeducation and offered a referral to a national hotline for counseling and support for IPV victims. In cases where the abuse of the victim is observed by children, the provider is reminded in the documentation tool to immediately refer the case to state child protective services, as required by law, and contact information was given.

To prepare clinics for participation, we will work with the Primary Care Service Line Director, clinical leaders in clinics and staff to implement the study. We will provide manuals, trainings and online education for clinic staff and providers. Online training will be integrated with MUSC's MyQuest staff education system. Educational materials will include tip sheets on intimate partner violence and how to implement screening procedures, video demonstration of EHR use, as well as videos demonstrating suggested scripting for interactions with patients. During the initial week of the roll out, Epic research support personnel will be available in the clinics to help providers learn to use software modifications and to answer questions. Provider support for in-person individual IPV-related training and case consultations will be provided by two experts in IPV training and management through-out the implementation and operation of the study.

Data Sources/Collection

All data will be collected within the Epic EHR system.

Outcome measurement

The primary outcome measure for the study is the rate at which patients were screened for IPV across the clinics. This outcome is calculated as the share of patients who completed PVS questions from all eligible patients. The secondary outcome is the rate at which patients at risk for IPV are detected by screening procedures. The patient is flagged positive if they are positive on one of the three PVS questions (Table 1). Other outcomes are the severity of risk (using Danger 5 risk assessment, ranging from 0 to 5) observed in patients, physician compliance with IPV management tools (measured as the rate of completion of follow-up decision templates, and the rate of referrals for post-visit counseling to a national hotline (a share from screened positive patients).

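### The primary outcome counts only PVS completion, which the control condition does not offer, and the stated 97% power is for a different quantity

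*Combined protocol and SAP*

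**What the plan says.** Under Outcome measurement: "The primary outcome measure for the study is the rate at which patients were screened for IPV across the clinics". The next sentence gives the calculation: "This outcome is calculated as the share of patients who completed PVS questions from all eligible patients". Nurse-led screens do not enter it.

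The abstract lists as an intervention component "confidential screening using the 3-item Partner Violence Screening (PVS) instrument" and describes the comparator as "a control intervention of screening for IPV using nurse interviews and an electronic checklist". Study design/Participants adds: "The control condition is a nurse-led screen developed by MUSC and deployed in 2019". That screen rests on professional judgment and uses no standardized questions. Figure 1 heads the post-crossover columns "Intervention Start (nurse-led and confidential screen", and the text says of the two screens: "thus two screens are working at the same time during intervention period".

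The secondary outcome is the rate at which women at risk are detected. Its scoring sentence reads "The patient is flagged positive if they are positive on one of the three PVS questions (Table 1", yet the table it cites sets out positive and negative results for both screens.

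Power Calculations describes the control periods as steps without screening. It claims 97% power for a rise in screening from 0.14% to 5.5%, and 89% for referral from 0.14% to 3.9%. The same section gives 0.14% as the upper bound on the current referral rate, 5.5% as annual prevalence, and 95% as the expected screening completion rate. Statistical analysis specifies a logit mixed model with block, a fixed effect for each step and a random clinic effect.

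**The concern.** A between-condition primary outcome has to be one that either condition could produce. Completion of a questionnaire that exists in only one condition is a measure of uptake. The comparison is settled by the design, and the nurse-led control, which the protocol cites among its reasons for choosing a stepped wedge, contributes nothing to it. The primary result could not say whether more women are screened, or found at risk, than under nurse-led screening.

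The documents also disagree on whether the control is screening at all: the abstract, Figure 1 and Table 1 treat it as a screen, while Power Calculations does not. A reader therefore cannot tell which quantity the 97% describes.

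**Working it through.** **1. Control rate.** No section gives a PVS rate before crossover. The PVS is an intervention component, the control asks no standardized questions, and Figure 1 shows the confidential screen only after crossover. A rate of 0% is an inference from these three statements.

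**2. The model.** Take zero control events. Lower the intercept by c and raise the treatment coefficient by c. Every treated cell keeps its linear predictor, and every control cell moves further towards zero, which raises its likelihood. This holds at each value of the clinic effect, so the marginal likelihood also rises for every c > 0. There is no finite maximum, hence no finite odds ratio. A likelihood-ratio test or a risk difference can still be computed.

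**3. The plan's power figures.** A parallel-cluster formula comes close to them. Inputs: 34,000 visits per condition, ICC 0.05, two-sided alpha 0.05 (all Power Calculations), and 2,400 visits per clinic (600 x 4 periods).
- Effective n = 34,000 / (1 + 2,399 x 0.05) = 34,000 / 120.95 = 281.
- Power = Φ{[|p1 − p2|√n − 1.96√(2p̄(1 − p̄))] / √(p1(1 − p1) + p2(1 − p2))}.
- 0.14% vs 5.5%: (0.899 − 0.459) / 0.231 = 1.90, power 97.2% (stated 97%).
- 0.14% vs 3.9%: power 88.9% (stated 89%).

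With 14 clinics of 600 visits per condition, n = 8,400 / 30.95 = 271 and the results are 96.7% and 87.8%. So the match does not identify the exact inputs used.

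**4. What the powered rates are.** 5.5% x 0.95 x 0.75 = 3.9%, which is the plan's second contrast: prevalence, times completion, times counselling. In that chain the 5.5% is prevalence and 95% is completion. Neither 0.14% nor 5.5% is a completion rate.

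**5. Stepped-wedge power.** Hussey-Hughes variance, with I = 28 clinics, T = 4 periods, 600 visits per clinic-period, ICC 0.05, and blocks of 9, 9 and 10 (assumed within the stated 8-12). Treated clinic-periods: U = 9 + 18 + 28 = 55. W = 9² + 18² + 28² = 1,189. V = 9 x 9 + 9 x 4 + 10 x 1 = 127.

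Var = Iσ²(σ² + Tτ²) / [(IU − W)σ² + (U² + ITU − TW − IV)τ²], with IU − W = 351 and the second bracket 873. Here τ² = 0.05 p̄(1 − p̄) and σ² = 0.95 p̄(1 − p̄) / 600.

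- Both of the plan's contrasts: over 99%.
- The outcome as defined, 0% vs 95%: near 100%.

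**6. Detection by either screen.** Intervention rate assumed to be 0.95 x 5.5% = 5.2%, which treats the PVS as perfectly accurate. The control rate is in no document, so a range is shown. Example at 4%: p̄ = 0.0461, τ² = 0.00220, σ² = 0.0000697, SE = 0.00298; 0.01225 / 0.00298 − 1.96 = 2.15, power 98%. The last column assumes a cluster autocorrelation of 0.8, which replaces σ² by σ² + 0.2τ² and τ² by 0.8τ².

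| Control rate | Stable clinic effects | Autocorrelation 0.8 |
|---|---|---|
| 2% | over 99% | over 99% |
| 3% | over 99% | 82-84% |
| 4% | 98% | about 33% |

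The 82-84% range covers different block sizes within 8-12.

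**The case against.** The best defence is that the comparison is already in the plan. The secondary outcome is detection, Table 1 scores both screens, and PVS uptake is a legitimate target for what the protocol calls dissemination research. Much of this stands. Uptake is worth reporting, and the secondary outcome read with Table 1 is nearly what is needed. But its scoring sentence admits PVS positives only, and uptake remains an intervention-period measure. Nor does Table 1 rescue the primary outcome: it defines who is positive, not who has been screened.

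Three stronger readings are tempting, and the documents do not support them.

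- *The trial is underpowered.* It is not for the outcome as defined, and the stepped-wedge formula gives over 99% for both stated contrasts.
- *The analysis is certain to break down.* The 0% is inferred and the model section does not name its outcome variable. A few forms filed before crossover would make the odds ratio finite, though it would then rest almost wholly on those forms.
- *The denominator is wrong.* The reminder is turned off for a year after a negative screen, so some women seen in later steps are not due. But Study design/Participants speaks of eligibility for the confidential screen, so eligible may already exclude them. The term is unclear, not shown to be in error.

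The remedy has a weakness too. Detection by either screen sets one screen against two, so extra positives, false ones included, are partly built in. The nurse item also covers abuse and neglect in general.

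**Conclusion.** The point holds, in this form. As written, the primary outcome cannot compare the two conditions: 0% (inferred) against an assumed 95%. The planned odds ratio has no finite value if there are no control events. The 97% power belongs to a contrast of current referral with prevalence, so it describes neither the primary outcome nor any other single quantity in the plan. This is an error of definition and labelling, not a shortage of clinics or patients.

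The conclusion about the outcome rests on reading the calculation sentence literally and on the PVS being absent before crossover. If nurse-led screens were meant to count, the text still needs correcting. Power for a replacement is less secure than the near-100% figure suggests: for detection it depends on an unstated nurse-positive rate and on how stable clinic effects are over time.

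**What to change.** 1. Report PVS completion as uptake, descriptively, in intervention periods.
2. For the between-condition comparison, use an outcome that can occur in both conditions. The closest is the existing secondary outcome: detection, scored by Table 1 for both screens, over all eligible women seen, with one counting rule in both conditions. Any documented screen is the alternative, although it credits a checklist completed without standardized questions. State that the intervention has two screens and the control one, that added positives are therefore partly built in, and that the nurse item is broader than partner violence. Report positives from each screen separately.
3. Correct the PVS-only scoring sentence for the secondary outcome. Reconcile the nurse item on excessive fear or guarded behaviour, which is positive in Study design/Participants and negative in Table 1. Say whether eligible includes women not due for a repeat within a year of a negative screen.
4. Relabel the 0.14% vs 5.5% contrast. Restate power for the chosen outcome with its own control rate from 2019 records (the nurse screen was in use that year), using the stepped-wedge variance and a range of control rates and autocorrelations.
5. The schedule ends in Q4 2021 and one reference is dated 2023, so state whether outcome data from Periods 0-3 had been seen. If they had, keep the primary outcome as the plan states it, report it as uptake, and label the both-condition comparison post hoc, with no restated prospective power claim.

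Cost: revised wording, one query of 2019 records and a new power calculation. All data come from the EHR, so no new collection is needed. The price is a much smaller contrast than 0% vs 95%, and one that counts screen positives, not confirmed cases.
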